7.7 EXTENT OF EXPOSURE

Exposure to LAMA/LABA combination treatment with Spiolto® Respimat® will be estimated as time from the day treatment is initiated till the last dose administrated by the patient or study completion. Days on treatment will be summarized using N, mean, SD, minimum, median and maximum. Frequency and percentage will be presented for extent of exposure in weeks.

7.8 SAFETY ANALYSIS

In general, safety analyses will be descriptive in nature and will focus on ADRs (serious and non-serious), fatal AEs and pregnancy at the beginning and at the end of the study. All safety analyses will be based on the treated set.

Listings for adverse events, serious adverse event, adverse drug reaction (serious and non-serious), fatal adverse events and adverse events leading to treatment discontinuation will be listed separately by SOC and PT.

Listing of the pregnant patients will be prepared separately.

7.8.1 Adverse events

Adverse events will be collected at the time points or visits as specified in the study protocol table 9.1.1 . AEs will be coded using the Medical Dictionary for Regulatory Activities (MedDRA) version 20.1 or higher. All AEs occurring from signing of ICF onwards until end of the study will be collected.

An AE is considered to be an adverse drug reaction (ADR) if either the physician who has reported the AE or the sponsor assesses its causal relationship between event and drug checked as ‘Yes’.

The frequency and percentage of AEs/SAEs, AE with fatal outcome and ADRs (serious and non-serious) will be tabulated by system organ class and preferred term.

Multiple overlapping or adjacent recordings (AE occurrence) of same AE are collapsed into one AE event if all AE attributes are identical (patient number, LLT, outcome, therapy, intensity, action taken, seriousness, reason for seriousness, causal relationship).

Two AE occurrences are considered to be time-overlapping if the start date of the second, later occurrence is earlier or equal to the end date of the first occurrence.

Two AE occurrences are considered to be time-adjacent if the start date of the second, later occurrence is one day later than the end date of first occurrence.

All AEs will be listed individually for each patients by system organ class (SOC) and preferred term (PT) assigned to the AEs.

No imputation is planned for missing AE data except for missing dates which will be handled according to BI standard⁽²⁾.

An overall summary of adverse events will be presented with counts and percentages.

Summary of adverse events will be based on frequency and percentage of patients.

Summary will be presented for adverse event (AE), adverse drug reaction (ADR), serious adverse drug reaction, adverse events (including AE, SAE, ADR and serious ADR) leading to treatment discontinuation and serious adverse event with other seriousness criteria included fatal AEs.

The frequency of patients with adverse events will be summarized by primary system organ class and preferred term. The system organ classes will be sorted by default alphabetically preferred terms will be sorted by frequency (within system organ class) in descending order. Duration of AE will be calculated as AE end date minus AE onset date +1. Both onset and end dates need to be present to calculate a duration. If AE end date is missing then AE duration will be set as missing.

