9. RESEARCH METHODS

9.1 STUDY DESIGN

This is a self-controlled non interventional study enrolling consented COPD patients who will be treated with Spiolto® Respimat® according to approved SmPC. The Patients will be enrolled consecutively and will be followed over an observational period of approx. 6 weeks. Data as listed in [Table 9.1.1](#) will be collected.

Baseline characteristics of eligible patients and provided Informed Consent but were not treated in the study will also be collected.

The intended Health Care Professionals (HCPs) are private practice physicians who are treating symptomatic and COPD patients every day, being aware that most of their patients suffer from the physical restrictions induced by the disease per se.

Study results will be used to document the effectiveness of Spiolto® Respimat® in improving the functional status of COPD patients impaired in activity of daily living (ADL). It will complement the results of a previous trial using the PF-10 (1222.56). The biggest advantage of the current proposal is that the CCQ is a very well-known and widespread questionnaire, which is also included in the GOLD guidelines [\[R17-3684\]](#) and is validated in Greek [\[R17-3682, R17-3681\]](#).

Table 9.1.1: Visit flow chart and data collection parameters

Parameter	Visit 1 baseline visit	Visit 2 approx. 6 weeks after baseline visit	Telephone contact 2 weeks after baseline visit
Informed Consent	X		
Inclusion / Exclusion Criteria	X		
Patient demographics (age, gender, height, and weight)	X		
Smoking history	X	X	
Start of COPD	X		
Number of exacerbations in the last 12 months	X		
Number of exacerbations leading to hospitalization in the last 12 months	X		
Past COPD therapies (6 months before Visit 1)	X		
COPD related and other relevant concomitant medication	X	X	
Concomitant diseases / Comorbidities	X	X	
Respimat® training (yes/no)	X		
COPD severity based on GOLD assessment1	X		

Table 9.1.1: Visit flow chart and data collection parameters (cont'd)

mMRC breathlessness scale, completed by the patient	X		
CCQ completed by the patient	X	X	
General condition of patient evaluated by Physician's Global Evaluation (PGE)	X	X	
Adverse Drug Reactions (serious and non-serious), fatal AE, pregnancy	X	X	X
Patient satisfaction with Spiolto® Respimat®, survey completed by the Patient (abbreviated PASAPQ part 1). Patient preference for who used HH in precedence (PASAPQ part 2).		X	

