11.2 ADVERSE EVENT AND SERIOUS ADVERSE EVENT COLLECTION AND REPORTING

The investigator shall maintain and keep detailed records of all AEs in their patient files.

Collection of AEs

The study design is of non-interventional nature and the study is conducted within the conditions of the approved marketing authorization. Sufficient data from controlled interventional trials are available to support the evidence on the safety and efficacy of the studied BI drug. For this reason, the following AE collection and reporting requirements have been defined.

The following must be collected by the investigator in the (e)CRF from signing the informed consent onwards until the end of the study:

- all adverse drug reaction (ADRs) (serious and non-serious),
- all AEs with fatal outcome

All ADRs, including those persisting after study completion must be followed up until they are resolved, have been sufficiently characterized, or no further information can be obtained.

The investigator carefully assesses whether an AE constitutes an ADR using the information below.

Causal relationship of adverse event

The definition of an adverse reaction implies at least a reasonable possibility of a causal relationship between a suspected medicinal product and an adverse event. An adverse reaction, in contrast to an adverse event, is characterized by the fact that a causal relationship between a medicinal product and an occurrence is suspected.

Medical judgment should be used to determine the relationship, considering all relevant factors, including pattern of reaction, temporal relationship, de-challenge or re-challenge, confounding factors such as concomitant medication, concomitant diseases and relevant history.

Arguments that may suggest a **reasonable causal relationship** could be:

- The event is **consistent with the known pharmacology** of the drug
- The event is known to be caused by or **attributed to the drug class**.
- A **plausible time to onset of the event** relative to the time of drug exposure.
- Evidence that the **event is reproducible** when the drug is re-introduced
- **No medically sound alternative etiologies** that could explain the event (e.g. preexisting or concomitant diseases, or co-medications).
- The event is typically **drug-related and infrequent in the general population** not exposed to drugs (e.g. Stevens-Johnson syndrome).

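### SAP 7.8.1 says all AEs are collected, but the protocol requires only ADRs, fatal AEs and pregnancies, so the AE, SAE and discontinuation-AE percentages may be incomplete

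*SAP*

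**What the plan says.** On timing, SAP 7.8.1 defers to the protocol: "Adverse events will be collected at the time points or visits as specified in the study protocol table 9.1.1". On scope it then says: "All AEs occurring from signing of ICF onwards until end of the study will be collected". It plans tables by system organ class and preferred term, and patient-level summaries, for AEs, SAEs, fatal AEs, ADRs and AEs leading to discontinuation. SAP 7.8 adds matching listings and sets the treated set as the population for all safety analyses.

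The protocol is narrower. Section 11.2 opens its collection rule with "The following must be collected by the investigator in the (e)CRF from signing the informed consent onwards until the end of the study" and then names two items: ADRs, whether serious or not, and AEs that end in death. The safety row of Table 9.1.1 reads "Adverse Drug Reactions (serious and non-serious), fatal AE, pregnancy". The analysis list in 9.7 and the eCRF source-data list in 9.10.2.1 have the same scope. The reporting table in 11.2 covers serious ADRs, not all SAEs. Section 11.2 also says "The investigator shall maintain and keep detailed records of all AEs in their patient files", but that is a duty about the site's own files.

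On causality, SAP 7.8.1 says "An AE is considered to be an adverse drug reaction (ADR) if either the physician who has reported the AE or the sponsor assesses" it as causally related. Protocol 11.2 says "The investigator carefully assesses whether an AE constitutes an ADR using the information below".

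**The concern.** The two documents describe the same period, from consent to end of study, but not the same set of events. SAP section 4, which lists changes to the planned analysis, declares no widening of AE collection. A reader who relies on the SAP sentence would take the AE, SAE and discontinuation-AE percentages as complete counts of what happened to treated patients. Under the protocol they are complete only for ADRs and fatal AEs. Beyond that they depend on which non-required events each site chose to enter, and Protocol 9.8 plans no regular source data verification.

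The SAP's ADR rule is also affected. It lets a sponsor assessment turn an AE into an ADR, but the sponsor can assess only events that were entered.

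**Working it through.** The documents state no AE rate, so there is no AE figure to reproduce. The check compares the texts and then converts missed patients into percentage points.

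**Step 1. Which events must be in the eCRF (Protocol 11.2, Table 9.1.1), and which SAP rows use them.**

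| Event | Entry required? | Rows exposed if not entered |
|---|---|---|
| ADR, serious or not | Yes | None |
| AE with fatal outcome, any causality | Yes | None |
| Non-fatal, non-serious AE judged unrelated | No | Any AE; discontinuation AE if treatment stopped |
| Non-fatal SAE judged unrelated | No | Any AE; SAE; discontinuation AE if treatment stopped |

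Protocol 9.3 and SAP 5.4 use a general phrase about adverse events and safety reporting at Visit 2. The safety items that follow it are again ADRs, fatal AEs and pregnancies, so it does not establish wider collection.

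**Step 2. How a missing entry enters the percentage.** The denominator is the treated set (SAP 7.8). A treated patient with no qualifying record is in the denominator and not in the numerator, and so counts as event-free. For each row:

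true % − shown % = 100 × (treated patients with a qualifying event but no qualifying event entered) / (treated-set size)

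The numerator cannot be negative, so this mechanism gives no shift or a downward one.

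**Step 3. Scale per patient.** The treated-set size is not given. I assume it lies between the two figures in Protocol 9.5, which agree with each other: 1170 / (1 − 0.10) = 1300.

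- 100 / 1300 = 0.077 percentage points per missed patient
- 100 / 1170 = 0.085 percentage points per missed patient

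**Step 4. The shortfall is specific to each row.** Suppose, for illustration only, that 13 patients each have an entered non-serious ADR and an unentered, unrelated, non-fatal SAE.

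- Any-AE row: these patients already count through the ADR, so the shortfall is 0.
- SAE row: 13 / 1300 = 1.0 points, or 13 / 1170 = 1.1 points.

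**Step 5. The sponsor part of the ADR rule.** Required non-fatal entries are already ADRs by the investigator's judgement. A sponsor assessment can therefore add only fatal AEs that the investigator judged unrelated, or unrelated events that a site entered without having to.

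**The case against.** The strongest reply is that SAP 7.8, directly above, says the safety analyses focus on ADRs, fatal AEs and pregnancy, so the disputed sentence may be only a loosely worded time window. That reading is possible, but the focus statement stands beside AE and SAE listings and tables and does not limit them.

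The second reply is that the consequence turns on CRF Final 4.0, which SAP section 3 cites and which is not available here. The protocol's rule sets a minimum. The SAP treats causal relationship as an attribute of each AE, which would fit a form that accepts unrelated events, although fatal AEs alone would need that field. This stands: the data may be complete. What can be said is that nothing in the protocol requires it.

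Third, the restriction is deliberate. Protocol 11.2 justifies it by the safety evidence already available from controlled trials, so the limit on sponsor review follows from the design and no SAP wording will remove it. That also stands, and it is why the remedy here is a footnote and not more data.

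Fourth, 1170 is the precision sample after drop-out, not a treated set, and treated patients who drop out stay in the treated set. That is fair. The range is an assumption, and the 13-patient case illustrates the arithmetic without estimating anything.

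Finally, reasons for stopping treatment are collected separately (Table 9.1.1; Protocol 9.7). This helps with the discontinuation row, but it does not require an AE record for an unrelated event.

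**Conclusion.** The concern holds, as a minor point. SAP 7.8.1 claims a wider collection than the protocol it cites. Completeness of the any-AE, SAE and discontinuation-AE rows is therefore not assured. Any error from this source is downward, at 0.077 to 0.085 percentage points per missed patient if the treated set is 1170 to 1300. The total cannot be computed without an AE rate, the share judged unrelated and the CRF content.

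Confidence is high that the texts disagree. Whether any event was actually left out is unknown. Investigator-assessed ADRs, fatal AEs and the CCQ outcomes are untouched. ADRs that only the sponsor would have recognised could be missed if the event was never entered. Safety is descriptive and no objective rests on total AE incidence, so this is a correction of scope and labelling.

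**What to change.** 1. Check CRF Final 4.0. Unless it required all AEs, replace the SAP 7.8.1 sentence with the scope of Protocol 11.2 and Table 9.1.1: ADRs (serious and non-serious), AEs with fatal outcome, and pregnancies.
2. Keep every entered event in the outputs, but title the AE, SAE and discontinuation-AE tables and listings *reported AEs (collection required only for ADRs and fatal AEs)*.
3. Add a footnote: entry of non-fatal unrelated AEs was not required, so these percentages are not total AE or SAE incidence, and sponsor causality assessment was possible only for entered events.
4. In the discontinuation-AE table, refer to the separately collected reasons for ending treatment. Protocol 9.7 lists these for analysis. The readable SAP sections cover them only through the general rule that all study data are listed, so confirm that the output exists.

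If the CRF did require all AEs, correct the mismatch in that direction and omit the labels.

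The cost is one CRF check, one SAP sentence, titles, a footnote, and possibly one short summary of stopping reasons. No new data are needed.

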7.8.2 Laboratory data

This section is not applicable as no laboratory data are planned to collect as per the CTP.

7.8.3 Vital signs

This section is not applicable as no vital signs data are planned to collect as per the protocol.

7.8.4 ECG

This section is not applicable as no ECG data are planned to collect as per the protocol.

7.8.5 Others

No other data is planned to collect as per protocol.

10 HISTORY TABLE

Table 10: 1 History table

Version	Date	Author	Sections Changed	Brief description of change
Final 1.1	26-July-2019		•Section 4, Section 7.5.1	• Section 4 updated as per amended protocol and secondary objective description updated.
Final 1.1	14-May-2019		•Section 5.2, Section 7.5	• Added secondary objective “Treatment continuation of Spiolto® Respimat® after the study” as per updated protocol version 2.0.
Final 1.0	12-Feb-2019		•	
Draft 1.3	10-Oct-2018		•Section 1 •Section5.1 Section7.4 Section7.5.1 •Section 5.4 •Section 6.2 •Section 7.4 Section 7.5.1	• Updated TSAP the latest version of TSAP display template • >0.4 is replace by ≥ 0.4 • Safety reporting text is repeated in section 5.5, so it was removed. • Added word “medical” for “Note: ... such as site monitoring or IPV that is too complex to program which identified by the trial medical team • Added following figures for primary and secondary endpoints Figure 15.2.1 Bar Graph of Number and Percentage of subjects achieved therapeutic success(Full Analysis Set) Figure 15.2.2 Bar Graph of Absolute change in Total CCQ Score(Full Analysis Set) Figure 15.2.3 Bar Graph of PGE Score at visit 1 and visit 2(Full Analysis Set) Figure 15.2.4 Bar Graph of Patients Satisfaction Score (PASAPQ Part I) at Visit 2 (Full Analysis Set) Figure 15.2.5 Bar Graph of

Version	Date	Author	Sections Changed	Brief description of change
				Patients' (who have used Spiriva HH prior to the study) Preference and Willingness to Continue with Inhaler (PASAPQ Part II) at Visit 2 (Full Analysis Set)
Draft 1.2	20-Sep-2018		
•Section 1•Section 6.3•Table 6.3: 1••Section 6.5•Section 7.8.1•Section 8	
• Updated TSAP the latest version of TSAP display template• List of table added under table of contents• Definition of patient analysis set has updated• Updated the table 6.3: 1 for more clarification•• Updated text for pooling of centres• Other significant adverse event removed from the adverse event analysis• Removed section 8.0
Draft 1.1	22-Jun-2018		
•Section 5.1•Section 5.2•Section 5.2.1•Section 5.4•Section 6.2•Section 6.3•Section 6.6•Section 7•Section 7.4•Section 7.5.1•Section 7.5.2•Section 7.8.1	
• Mentioned more specific primary and secondary outcomes under section 5.1 and 5.2• Removed section 5.2.1 as not applicable• Updated section 5.4• Updated analysis set to be excluded from for specific iPVs.• Updated patient analysis set under section 6.3• Handling of missing data and ambiguous values for the calculation of CCQ score updated under section

Version	Date	Author	Sections Changed	Brief description of change
				
6.6
 
• Section 7 updated for the numeric presentation of data• Section 7.4 updated for the method to calculate CCQ score• Section 7.5.1 removed as not applicable• More measurement details specified for secondary outcomes under section 7.5.2• Added definition of other significant adverse event under section 7.8.1
Draft 1.0	03-April-2018		None	This is the initial TSAP with necessary information for trial conduct
